6.1.2 Use of Study Device

Use of device will be documented on case report forms for each subject. Any unused devices must be returned to the Sponsor at the end of the study or before product expiration date.

6.1.3 Return or Destruction of Study Device

At the completion of the study, there will be a final reconciliation of study devices shipped, devices used, and devices remaining. This reconciliation will be logged on the device accountability log. Any discrepancies noted will be investigated, resolved, and documented prior to return or destruction of unused study devices. Devices destroyed on site will only be upon written instruction from the sponsor and will be documented in the study files.

6.1.4 Device Deficiencies

Device deficiencies are defined as the inadequacy of a medical device with respect to its identity, quality, durability, reliability, safety or performance. Record all device deficiencies on the case report form and report to the Sponsor.

7 OVERALL STUDY PROCEDURES

7.1 Informed Consent and Screening Procedure

7.1.1 Full written informed consent will be obtained for all subjects prior to enrollment in the study.

7.1.2 During the COVID19 pandemic, subjects will be asked to wear a face mask when they arrive at the research site.

7.1.3 In Stage 1, a screening blood pressure measurement will be taken for all consented subjects during the day of data collection. Subjects must meet the blood pressure requirements in order to be enrolled in the study. Subjects with screening blood pressure outside the Stage 1 values will be removed from the study as screen failures.

Screening Blood Pressure Values		
	Systolic	Diastolic
Hypertensive	> 140 mmHg	> 85mmHg
Hypotensive	< 100 mmHg	< 60 mmHg

7.1.4 In Stage 2, screening procedures for subjects will include a measurement of subjects' upper arm circumference. Subjects will be categorized into bins for the Masimo blood pressure cuff used, according to the table below. The Masimo blood pressure cuff sizes are: Small (20-26 cm), Medium (25-34 cm) and Large (32-43 cm).

	Small		Medium		Large	
Upper Arm Circumference	20-23 cm	23-26 cm	25-29.5 cm	29.5-34 cm	32-37.5 cm	37.5-43 cm

- Subjects may be removed from the study as screen failures if their arm circumference falls into a bin that has had sufficient enrollment.

7.2 Study Procedure

7.2.1 Ensure the subject is in a relaxed and comfortable position, either seated or lying down, with the arm at heart level and legs uncrossed. Subject should be in the same position for at least 5 minutes prior to blood pressure measurement. During that time, subject demographics and health history may be completed in the CRF.

7.2.2 [REDACTED].

7.2.3 Measure arm circumference and place the appropriate size cuff preferably on the left arm of the subject. The middle of the cuff should be at same level as the heart, see Figure 8. Do not place cuff on an extremity selected for IV infusions or any other intravascular access, e.g. dialysis.

7.2.4 Perform an auscultatory measurement. See section 7.3 for details on the auscultatory measurement procedure (reading R_0 in Figure 7).

7.2.5 Wait at least 60 seconds to allow venous blood flow to normalize.

7.2.6 [REDACTED].

7.2.7 Perform [REDACTED] blood pressure measurement procedure (T_0 in Figure 7).

7.2.8 Wait at least 60 seconds to allow venous blood flow to normalize.

7.2.9 Remove the Masimo cuff and automated blood pressure device and replace with the reference auscultatory cuff and stethoscope.

7.2.10 Perform an auscultatory measurement (R_1 in Figure 7).

7.2.11 Repeat 7.2.5-7.2.10 until at least four valid automated and auscultatory measurement pairs have been performed or eight measurement pairs have been attempted.

- A measurement pair is considered valid if the observer difference criteria in 7.3.4 is satisfied and the automated blood pressure device performs a successful measurement.
- Counting begins with measurement pair T_0-R_1 (e.g. $T_0-R_1, T_1-R_2, T_2-R_3 \dots$ maximum up to T_7-R_8 . See Figure 7).

7.2.12 If less than four paired measurements are obtained after eight paired attempts, subject participation in the study will end.

7.2.13 Be sure to check cuff site health and integrity between measurements.

7.2.14 Disinfect auscultatory blood pressure cuff and allow to air dry, per manufacturer's cleaning directions, after use with each patient.

7.2.15 No treatment decisions will be made based on blood pressure results from study devices.

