3 STUDY DESIGN

This is a prospective, nonrandomized multi-center study, which is based on the ISO standard 81060-2:2018 for the investigation of noninvasive sphygmomanometers.

The study will be conducted at two sites where noninvasive blood pressure measurements will be [REDACTED]

[REDACTED]
[REDACTED]

The study will be conducted [REDACTED] to meet the blood pressure distribution requirements and the limb size distribution requirements in the ISO 81060-2:2018.

[REDACTED] Site 1 [REDACTED] will enroll [REDACTED] patients from among the physician's patients. Site 2 [REDACTED] volunteers.

[figure not shown]

Figure 4: Blood pressure distribution (ISO 81060-2:2018)

Stage 2 will begin after the minimum subjects have been enrolled in the study to meet the blood pressure distribution requirements. Stage 2 will satisfy the cuff distribution requirements of ISO 81060-2:2018. Each cuff size will be tested as per requirements of ISO 81060-2:2018.

Cuff size	Upper half of range of cuff size	Lower half of range of cuff size
Small, Medium, Large	40% of subjects	40% of subjects

Figure 5: Cuff size distribution (ISO 81060-2:2018)

Blood pressure measurements will be obtained using the Masimo NIBP device and also obtained using the auscultatory method as a reference. Each value from the Masimo device will be paired with two measurements from two observers using the reference auscultatory technique, for a total of 4 successful paired measurements per subject. A pair is considered valid if both observers' SBP and DBP readings are within 4 mmHg and the prototype successfully measures.

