7.3 Auscultatory Blood Pressure Measurement Procedure

7.3.1 Place the bell of the stethoscope on the brachial artery. Remind subject to refrain from speech and excessive movement during measurement. Two qualified observers, who may be research staff, will listen to the Korotkoff sounds using the ear pieces of the stethoscope. See Figure 9.

[figure not shown]

Figure 9. Auscultatory blood pressure measurement using a stethoscope.

7.3.2 Connect inflation pump to the cuff and inflate to 20-30 mmHg above the systolic pressure, the point at which radial pulse is no longer audible.

7.3.3 Deflate cuff slowly at a rate of approximately 2-3 mmHg/sec. Each observer will listen to Korotkoff sounds and record the systolic and diastolic values independently on a data collection sheet; observers will be blinded to each other's reading and will be provided with their own data collection sheet or will be recording the measurements on independent electronic forms. Observers should avoid parallax errors when reading the pressure gauge by orienting their line of sight directly above the gauge.

7.3.4 A research coordinator will obtain the blood pressure results from each observer's data collection sheet, and will record the values into the paper case report form (CRF). The coordinator will compute the results from the readings and confirm if the paired measurement is valid. A valid measurement is when the observers' blood pressure values are within 4mmHg ($|\text{Observer1 Systolic} - \text{Observer2 Systolic}| \leq 4\text{mmHg}$, and $|\text{Observer1 Diastolic} - \text{Observer2 Diastolic}| \leq 4\text{mmHg}$). If an electronic CRF is being used, difference between the Observer1 and Observer2 readings will be performed by the system.

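### The health history may be taken during the 5 minutes before the first reading; if pressure is still settling afterwards, the fixed device-then-reference order carries that drift into the measured difference

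*Combined protocol and SAP*

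**What the plan says.** Section 7.2.1 wants the subject relaxed and comfortable, and sets a minimum period: "Subject should be in the same position for at least 5 minutes prior to blood pressure measurement". The next sentence gives those minutes a second use: "During that time, subject demographics and health history may be completed in the CRF".

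Speech is mentioned in one visible place, 7.3.1: "Remind subject to refrain from speech and excessive movement during measurement". That covers the auscultatory reading, not the minutes before it.

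The series starts with an auscultatory reading, R_0. Then come a wait ("Wait at least 60 seconds to allow venous blood flow to normalize"), the device reading T_0, a second wait of the same minimum length, a change of cuff, and the reference R_1. On which readings count, 7.2.11 says: "Counting begins with measurement pair T_0-R_1". The sequence continues T_1-R_2 and so on, up to T_7-R_8. Section 3 asks "for a total of 4 successful paired measurements per subject". Section 2 expresses the result as the mean and standard deviation of the difference. Section 8 leaves the analysis and the acceptance criteria to the ISO standard.

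**The concern.** As far as can be seen, a site can follow the protocol exactly while the subject answers questions until shortly before the cuff goes on. The subject has then held one position for 5 minutes but has not necessarily been quiet.

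This would matter little if device and reference were read at the same moment, or in alternating order. They are read one after the other, at least 60 seconds and a cuff change apart, and always in the same order within a counted pair. Any trend in true pressure over the series is therefore recorded as a difference between the methods. Where pressure is falling, the error tends to have the same sign from subject to subject, so enrolling more than the minimum of 85 would not average it away. It also makes a subject's four pairs differ for reasons unrelated to the device, which adds to the standard deviation.

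**Working it through.** The plan has no figure of its own to reproduce here: the minimum of 85 is taken from the standard and is not in dispute. The check traces the order of readings and then sizes the possible drift.

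**Inputs from the documents.** At least 5 minutes in position, with history-taking allowed (7.2.1); waits of at least 60 seconds before and after the device reading (7.2.5, 7.2.8); device first in each counted pair (7.2.11); four valid pairs per subject (Section 3).

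**Assumptions, not in the documents.** Talking raises systolic pressure by A = 5, 10 or 15 mmHg. After talking stops, the rise decays as A·exp(−t/τ), with τ = 2, 5 or 10 minutes. R_0 is at 0.5 min, device readings are at 3, 9, 15 and 21 min, and the references that follow are at 6, 12, 18 and 24 min.

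**Formulas.** With d(t) = A·exp(−t/τ):
- Following reference: shift = d(T_i) − d(R_i+1).
- Average of the references on either side: shift = d(T_i) − [d(R_i) + d(R_i+1)]/2.

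**Worked case, A = 10, τ = 5, following reference.**
- Pair 1: 10(e^−0.6 − e^−1.2) = 5.488 − 3.012 = +2.48
- Pair 2: 10(e^−1.8 − e^−2.4) = 1.653 − 0.907 = +0.75
- Pair 3: 10(e^−3.0 − e^−3.6) = 0.498 − 0.273 = +0.22
- Pair 4: 10(e^−4.2 − e^−4.8) = 0.150 − 0.082 = +0.07
- Mean: 3.52/4 = +0.88 mmHg. The SD across the four pairs is about 1.1 mmHg.

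With averaged references, pair 1 becomes 5.488 − (9.048 + 3.012)/2 = −0.54, and the four-pair mean is −0.24.

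**All nine scenarios (mmHg).** The last column adds 5 quiet minutes, which multiplies every shift by exp(−5/τ): 0.08, 0.37 or 0.61 for τ = 2, 5 or 10.

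| A | τ | Pair 1, following | Mean, following | Pair 1, averaged | Mean, averaged | Mean, following, 5 quiet min |
|---|---|---|---|---|---|---|
| 5 | 2 | +0.87 | +0.23 | −0.96 | −0.26 | +0.02 |
| 5 | 5 | +1.24 | +0.44 | −0.27 | −0.12 | +0.16 |
| 5 | 10 | +0.96 | +0.48 | −0.05 | −0.05 | +0.29 |
| 10 | 2 | +1.73 | +0.46 | −1.91 | −0.52 | +0.04 |
| 10 | 5 | +2.48 | +0.88 | −0.54 | −0.24 | +0.32 |
| 10 | 10 | +1.92 | +0.97 | −0.09 | −0.11 | +0.59 |
| 15 | 2 | +2.60 | +0.68 | −2.87 | −0.78 | +0.06 |
| 15 | 5 | +3.71 | +1.32 | −0.81 | −0.36 | +0.48 |
| 15 | 10 | +2.88 | +1.45 | −0.14 | −0.16 | +0.88 |

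With the following reference, the mean shift is under 1 mmHg in seven of nine scenarios, and the first pair is always the largest. With averaged references it is under 1 mmHg in all nine. There the first pair is largest for τ = 2 and 5; for τ = 10 all pairs are below 0.3 mmHg.

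**Second timing.** Here a reference reading takes 45 s, a device cycle 30 s and a cuff change 0 to 1 min; talking ends 0 to 2 min before R_0; A = 5 or 10; τ = 1, 2, 5 or 10. The four-pair mean is +0.01 to +0.88 mmHg with the following reference and −0.07 to −0.90 with averaged references. The first pair, following reference, is +0.04 to +2.20.

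**The case against.** Much of the case on the other side stands.

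- Completing an entry in the CRF need not mean an interview; part of the history could come from office charts, which Section 10.2 lists as source documents. A spoken history is a reasonable inference, but the text does not state it.
- Arm measurement and cuff placement come before R_0. R_0 opens no counted pair, and at least 60 seconds separate it from T_0. Talking right up to the first counted reading is therefore not what the procedure describes, and any carry-over is weakened.
- Steps 7.2.2 and 7.2.6, the body of 7.4 and Figure 7 cannot be seen, and any of them could ask for quiet. If one does, 7.2.1 as worded would still need reconciling with it.
- The rise, its decay and the timings are all assumed.

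Three stronger readings are tempting, and the documents do not support them. A reader might take 7.3.1 as the protocol's own statement that speech disturbs pressure. It gives no reason, and it sits beside the instructions on listening for Korotkoff sounds, where noise would explain it equally well. Nor does 7.2.1 say that the 5 minutes are meant to stabilise pressure. A reader might infer that the device will always read high. That holds only if each device reading is compared with the reference that follows. The numbering of the pairs in 7.2.11 suggests this, but Section 8 leaves the analysis to a standard that is not reproduced, and averaged references reverse the sign. Finally, a reader might suspect confounding with Site 1 and the high-pressure range. Nothing says histories are longer there; in Stage 1 that site recruits both hypertensive and hypotensive subjects, and in Stage 2 it has no pressure criterion.

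**Conclusion.** The point holds as a modest, avoidable weakness. The visible text lets the pre-measurement minutes be used for history-taking, and the fixed order within counted pairs turns any remaining trend in pressure into an apparent device difference. Under the assumed rise and decay, the four-pair mean moves by about 0 to 1.5 mmHg in either timing, mostly by less than 1 mmHg. The direction depends on how the reference value is formed. The conclusion requires that the history is spoken, that pressure has not settled by T_0, and that no unseen step already asks for quiet. Whether a shift of this size could change the outcome against the two accuracy criteria cannot be judged, because their limits are not in the documents. The case for acting is the very low cost, not a demonstrated threat to the result.

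**What to change.** Replace the last sentence of 7.2.1 with:

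> Complete demographics and health history before the 5-minute rest begins or after the last measurement. During the 5-minute rest and between readings, conversation with the subject is kept to what is needed for the procedure and to report discomfort or other symptoms.

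The exception matters: Section 1.3 relies on staff removing the cuff if the subject has discomfort, so complete silence through as many as eight pairs would be unsuitable. If a step that cannot be seen already addresses talking, align the two.

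The cost is at most about 5 minutes in a visit that Section 5.4 puts at 1 to 2 hours, or none if the history is taken after the last reading. Sample size, pairing and analysis are unchanged. Five quiet minutes reduce the drift without always removing it: at τ = 10 about 61% remains, so the largest modelled mean falls from 1.45 to 0.88 mmHg. Taking the history after the last reading removes this source altogether.

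### Does counting each device reading only against the auscultatory reading that follows it leave the reference value undefined?

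*Combined protocol and SAP*

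**What the plan says.** Section 7.2 sets the order R_0 (7.2.4), T_0 (7.2.7), R_1 (7.2.10), and then repeats the cycle. Each cycle contains two pauses with the instruction "Wait at least 60 seconds to allow venous blood flow to normalize". The cycle continues "until at least four valid automated and auscultatory measurement pairs have been performed or eight measurement pairs have been attempted".

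On validity, 7.2.11 says "A measurement pair is considered valid if the observer difference criteria in 7.3.4 is satisfied", and it adds that the device must have measured successfully. On counting it says "Counting begins with measurement pair T_0-R_1", running up to T_7-R_8. Section 7.2.12 closes the subject's participation when the quota is missed: "If less than four paired measurements are obtained after eight paired attempts, subject participation in the study will end".

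Section 7.3.3 has each observer record every systolic and diastolic value. In 7.3.4 the two observers must agree within 4 mmHg on both pressures, and "The coordinator will compute the results from the readings and confirm if the paired measurement is valid". Section 3 matches each device value with two measurements from two observers. Section 8 hands the whole statistical analysis to ISO 81060-2:2018. In the public version Figure 7 is not shown, 7.2.6 is redacted, and nothing can be read under the 7.4 heading.

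**The concern.** A design that brackets each test reading with two reference readings suggests that the reference is their average, because averaging cancels a steady drift in pressure. The counting rule does not require this. It tests R_(i+1) for the pair T_i-R_(i+1) and attaches no consequence to a failed R_i, or to a failed R_0 at the start. The phrase in section 3 about two measurements from two observers can be read as one reading by each observer, or as two successive readings.

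Two things could be at stake. If only the later reading is the reference, the device always comes first, so a common fall in pressure appears as positive device error. The rest period ("Subject should be in the same position for at least 5 minutes prior to blood pressure measurement") limits early settling but not drift over later cycles. If both readings form the reference, staff could close a subject at four counted pairs although one of those pairs rests partly on a reading that failed the 4 mmHg check. The mean and SD of the difference (section 2) and the two accuracy criteria (section 8) depend on this reference.

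**Working it through.** **The plan's own figure.** Pairs T_i-R_(i+1) for i = 0 to 7 give 8 pairs, which matches the stated maximum. They use 8 device readings and R_1 to R_8. With R_0 there are 9 auscultatory readings, so R_0 is the only one outside every counted pair. Each of R_1 to R_8 is tested once, as the later member of its pair.

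**Inputs.** The documents give no drift, reading SD or failure rate. Everything below except 4 pairs, 8 attempts and 85 subjects is an assumption, with failures taken as independent.

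**Case 1: only the later reading is the reference.** Let pressure fall by d per cycle and let T sit at fraction f of the gap between the two reference readings.
- Bias of device minus reference: (1 - f)d for the later reading, (0.5 - f)d for the bracketing mean.
- With f = 0.5 and d = 1 or 2: +0.5 or +1.0 mmHg, against 0.
- With f = 0.4: +0.6 or +1.2, against +0.1 or +0.2. With f = 0.6: +0.4 or +0.8, against -0.1 or -0.2.

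For the SD, let the device add e = 4 mmHg and let a reading vary with SD s = 3, 5 or 6.
- Single pair: sqrt(e² + 2s²) = 5.8, 8.1, 9.4, against sqrt(e² + 1.5s²) = 5.4, 7.3, 8.4 with bracketing (7 to 12% larger).
- Mean of four pairs: sqrt(e²/4 + s²/2) = 2.92, 4.06, 4.69, against sqrt(e²/4 + s²/4 + 3.5s²/16) = 2.87, 3.96, 4.57 (2 to 3% larger).
- If drift per cycle also differs between subjects with SD 2 mmHg, the later-reading SD of subject means is 3.08, 4.18, 4.80 (5 to 8% larger).

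**Case 2: both readings form the reference.** Let p be the chance that a reference reading passes the 4 mmHg check, with no device failures. A completed subject has no affected pair only if R_0 to R_4 all pass. The affected share of completers is therefore 1 - p⁵/P(complete), where P(complete) is the probability of at least 4 successes in 8 with chance p.
- p = 0.98: 1 - 0.904/1.000 = 9.6%, about 8 of 85 subjects.
- p = 0.95: 1 - 0.774/1.000 = 22.6%, about 19 of 85.
- p = 0.90: 1 - 0.5905/0.9996 = 40.9%, about 35 of 85.

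Among all 85 × 4 = 340 counted pairs, about 8, 21 or 42 are affected.

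**What a stricter count would do.** Full enumeration of the pass/fail sequences, counting a pair only if both bracketing readings pass, gives (no device failures):

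| Reference failures | Not reaching 4 pairs, as written | Not reaching 4 pairs, both required | Affected subjects who still reach 4 fully valid pairs |
|---|---|---|---|
| 2% | 0.0% | 0.0% | 99.6% |
| 5% | 0.0% | 0.5% | 97.7% |
| 10% | 0.0% | 3.5% | 91.6% |
| 20% | 1.0% | 18.8% | about 73% |

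At 20%, enrolment for 85 completers would be 85/(1 - 0.188), about 105, against 85/(1 - 0.010), about 86.

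**Which case does the text support?** Section 7.2.11 names one T and one R per pair, eight times over. Section 3 follows its phrase about two measurements with a validity rule that compares the two observers. Under 7.3.3 both observers listen to the same deflation. The natural sense is one reading by each observer, which is case 1. Nothing readable states case 2, although the standard or Figure 7 might.

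**The case for a change.** The strongest reply is that delegating the calculation to a standard does not tell site staff when to stop. If the standard's calculation uses both bracketing readings, the bedside count checks only one of them. A subject who leaves at four counted pairs cannot be recalled, and at failure rates up to 10% over nine in ten of the affected subjects would have reached four fully valid pairs within the eight attempts already allowed. One linking sentence would cost little.

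Part of this stands. The readable text does not define the reference value, and fixing such a definition before the data are seen is good practice. The rest depends on a calculation that the documents do not state. The four pairs in 7.2.11 and the 85 subjects in section 5.1 are floors, so further pairs or subjects are allowed. Section 7.2.12 only ends participation; it does not say that a subject with fewer fully valid pairs is lost to the analysis. The stricter count also works least well where failures are common: at 20% it leaves 18.8% of subjects incomplete instead of 1.0%.

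**Conclusion.** No change follows. The description of the rule is right: R_0 is in no counted pair, and a failed earlier reading does not void the pair that follows it. Whether that is a fault depends on a definition that section 8 assigns to the cited standard and that Figure 7 or the redacted steps may also give.

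If the standard uses the later reading, 7.2.11 already agrees with it and the primary result is unaffected. The order effect is then a modest feature of the design: 0.4 to 1.2 mmHg in the mean under an assumed fall of 1 to 2 mmHg per cycle, and 2 to 3% in the SD of subject means without between-subject drift. It can be inspected afterwards from the recorded readings. If the standard uses both readings, the analysts would compute the reference that way and could identify each failed earlier reading, because 7.3.3 and 7.3.4 put every observer value on record. What remains is a shortfall of fully valid pairs, affecting 9.6 to 40.9% of completers at assumed failure rates of 2 to 10%.

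The documents establish neither case, and no accuracy limit is readable against which to judge pass or fail. The point is a definition left to the standard, which analysts can supply from it.

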9 SAFETY AND ADVERSE EVENTS

9.1 Definitions

The definitions for adverse event, adverse device effect, serious adverse event, serious adverse device effect, and unanticipated adverse device effect are provided below (ISO 14155:2011, 21 CFR 812.3(s)).

- **Adverse Event (AE):** an adverse event is any untoward medical occurrence in a subject which need not be related to the device under investigation.
- **Adverse Device Effect (ADE):** an adverse device effect is any untoward or unintended response to a medical device which may result from insufficiencies in the instructions for use or deployment of the device, or from use error.
- **Serious Adverse Event (SAE):** a serious adverse event is an adverse event that results in death, inpatient hospitalization, severe or permanent disability, a life threatening illness or injury, fetal distress, fetal death, a congenital abnormality, a birth defect, or medical or surgical intervention to prevent permanent impairment to body or structure.
- **Serious Adverse Device Effect (SADE):** a serious adverse device effect is an adverse device effect that results in death, inpatient hospitalization, severe or permanent disability or is life threatening.
- **Unanticipated Adverse Device Effect (UADE):** any serious adverse effect on health or safety or any life threatening problem or death cause by or associated with, a device, if the effect, problem, or death was not previously identified in nature, severity or degree of incidence in the investigational plan, or application (including a supplementary plan or application) or any other unanticipated serious problem associated with a device that related to the rights, safety or welfare of subjects. Refer to the Device Risk Analysis and Risk Assessment section in the investigator's brochure for details on anticipated adverse device effects.

9.2 Anticipated Adverse Events:

- Subject may feel slight discomfort temporarily during blood pressure cuff inflation.
- Bruising may be possible in some subjects.
- Subject may develop possible ischemia, purpura, and/or neuropathy at the site of the cuff or at the extremity. Cuff site will be inspected by research staff throughout measurements for any signs of adverse events. Subject participation will be stopped if adverse events are observed.

9.3 Adverse Event Reporting:

- All Adverse Events, both Anticipated and Unanticipated, must be recorded in the within the CRF and in the Adverse Event Report Form.

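### The measurement series runs on to eight attempts after a fifth void pair has already put the required four valid pairs out of reach

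*Combined protocol and SAP*

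**What the plan says.** Section 3 describes the data wanted from each subject: device values paired with two-observer auscultatory readings, "for a total of 4 successful paired measurements per subject".

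Section 7.2.11 gives the stopping rule. The steps are repeated "until at least four valid automated and auscultatory measurement pairs have been performed or eight measurement pairs have been attempted". On numbering it says "Counting begins with measurement pair T_0-R_1", with T_7-R_8 as the last possible pair, so the opening auscultatory reading R_0 lies outside the count. Section 7.2.12 gives the consequence of falling short: "If less than four paired measurements are obtained after eight paired attempts, subject participation in the study will end".

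A pair is valid when the two observers agree within 4 mmHg on both pressures and the device gives a reading (7.2.11, 7.3.4). Under 7.3.4 the coordinator confirms validity; with an electronic form, the system computes the observer difference.

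Two other places bear on the point. Section 5.6.1 lists failure on protocol requirements among the reasons for withdrawal, and 5.6.2 permits data gathered up to withdrawal to enter the final analysis. Section 9.2 lists the anticipated cuff effects, among them: "Subject may develop possible ischemia, purpura, and/or neuropathy at the site of the cuff or at the extremity".

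**The concern.** The rule has an upper limit on attempts but no stop for the case where the target can no longer be met. Staff must keep a running count of valid pairs to apply 7.2.11 at all, so they know at once when a fifth void has occurred. As written they still continue to the eighth attempt.

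Each further attempt means another device reading, another auscultatory reading, cuff changes and two waits of at least 60 seconds (7.2.5, 7.2.8). These attempts fall on subjects in whom the device reading or the observers' agreement has already failed five times. Section 1.3 states that subjects gain no direct benefit. At stake is a modest, avoidable exposure to cuff inflation, and an unanswered question about what the extra pairs are for.

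**Working it through.** **Inputs**

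- Target: 4 valid pairs (section 3, 7.2.11).
- Limit: 8 attempted pairs (7.2.11). The labels T_0-R_1 to T_7-R_8 also give 8 pairs, so the plan's own figure is reproduced.
- Inflations: 1 for R_0, then 1 automated and 1 auscultatory per attempt. One inflation per automated reading is an assumption: 7.2.6 and part of 7.2.7 are redacted, Figure 7 is not available and 7.4 is only a heading. It is also assumed that the auscultatory reading is still taken when the device reading fails.
- Void rate: not given in the documents. A range is used, with pairs treated as independent.

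**Point of no return**

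With v void pairs, at most 8 − v of the eight can be valid. Four valid pairs need 8 − v ≥ 4, that is v ≤ 4. The fifth void makes four impossible.

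**Further inflations after that point**

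A full series is 1 + 2 × 8 = 17 inflations. If the fifth void falls at attempt k, 1 + 2k have been done and 2 × (8 − k) remain.

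| Fifth void at attempt | Inflations done | Inflations still to come |
|---|---|---|
| 5 | 11 | 6 |
| 6 | 13 | 4 |
| 7 | 15 | 2 |
| 8 | 17 | 0 |

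The maximum of 6 is 6/17 = 35% of the full series. It occurs only when the first five pairs are all void.

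**How often, and how many on average**

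Let p be the chance that a pair is valid and q = 1 − p. The fifth void falls at attempt k with probability C(k−1, 4) q^5 p^(k−5), for k = 5 to 8. The sum over k is P(fewer than four valid pairs). The mean number of further inflations among those subjects is the sum of 2(8 − k) times each probability, divided by that total.

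Worked for p = 0.5: the four probabilities are 0.0313, 0.0781, 0.1172 and 0.1367, which sum to 0.363. The weighted sum is 6 × 0.0313 + 4 × 0.0781 + 2 × 0.1172 = 0.734, and 0.734 / 0.363 = 2.0.

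| Assumed p | P(fewer than four valid) | Mean further inflations among those subjects | Such subjects per 85 |
|---|---|---|---|
| 0.9 | 0.0004 | 1.1 | 0.04 |
| 0.8 | 0.010 | 1.3 | 0.9 |
| 0.7 | 0.058 | 1.5 | 4.9 |
| 0.5 | 0.363 | 2.0 | 30.9 |
| 0.3 | 0.806 | 3.1 | 68.5 |
| 0.1 | 0.995 | 4.9 | 84.6 (85 × 0.995) |

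Over 85 subjects, the total of further inflations is 85 × 0.734 = 62 at p = 0.5, 85 × 0.0843 = 7.2 at p = 0.7 and 85 × 0.0132 = 1.1 at p = 0.8.

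The lowest rows cannot describe a whole study that succeeds in collecting its data. They are informative for single subjects in whom readings keep failing. If voids cluster in a few subjects, the mean among those who fall short moves towards the lower rows.

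**The case against.** A reader might infer that the extra inflations serve no purpose at all. The documents do not support that. After five straight voids, attempts 6 to 8 can still give up to three valid pairs. No section says that pairs from a subject with fewer than four are discarded, and 5.6.2 may let them in. Section 3 states a total per subject but sets no exclusion rule, and section 8 leaves the analysis to the ISO standard, which is not reproduced in the plan. This objection stands: the supportable statement is that the later attempts cannot complete the set of four.

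A reader might also take six as the usual number. It is the worst case, with probability 0.031 at p = 0.5 and 0.0024 at p = 0.7. At success chances of 0.8 or more, hardly any subject is affected.

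Nor is this a case of an unprotected subject. Sections 1.3, 7.2.13, 9.2 and 5.6.1 provide for cuff removal on discomfort, site checks, stopping on adverse events, and withdrawal at any time. The over-pressure risk in section 1.3 is tied to the automated readings, so it applies to only half of the further inflations. These safeguards limit the harm, but most respond to a problem that has already appeared; none removes attempts that cannot reach the target.

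Finally, 7.2.11 and 7.2.12 agree with each other, and a fixed limit of eight is simple to run. That is true, but a count of void pairs is no harder to keep, because the running count of valid pairs is needed anyway.

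**Conclusion.** The point holds as a minor improvement. Sections 7.2.11 and 7.2.12 carry the series to eight attempts after the fifth void pair has made four valid pairs impossible. Subject to the assumptions above (one inflation per automated reading, an auscultatory reading at every attempt), that is 6, 4 or 2 further inflations when the fifth void comes at attempt 5, 6 or 7.

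Among subjects who fall short, the mean is between 1.1 and 4.9 over assumed success chances from 0.9 down to 0.1. The study-wide burden is small unless voids are common. The void rate and the independence of pairs are assumptions, and the redacted steps could change the inflation count.

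The second part is a gap in the text: whether one to three valid pairs from such a subject are analysed is left open between section 3 and 5.6.2.

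**What to change.** Amend 7.2.11–7.2.12 so that the series ends at four valid pairs or at the fifth void pair, whichever comes first. The limit of eight then follows by itself, since a series still open after seven attempts has three valid and four void pairs, and the eighth settles it. Record the number of attempted and void pairs for each subject.

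In the same edit, reconcile 7.2.11–7.2.12, section 3 and 5.6.2 by stating whether pairs from subjects with fewer than four valid pairs enter the analysis.

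The cost is a sentence or two. No subject who could still reach four valid pairs is affected. The downside is the loss of up to three possible valid pairs in subjects who cannot reach four, which matters only if partial sets are analysed. If the sponsor does intend to use them, the protocol should say so, as that would be the reason for continuing to eight. This is a rule about data collection; 7.2.15 already keeps study readings out of treatment decisions.
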